3.0 DRUG INFORMATION

There is no drug information for this study.

4.0 STAGING CRITERIA (AJCC SEVENTH EDITION, 2010)

Primary Tumor (T)

T2 Tumor invades muscularis propria

 pT2a Tumor invades superficial muscularis propria (inner half)
 pT2b Tumor invades deep muscularis propria (outer half)

T3 Tumor invades perivesical tissue

 pT3a Microscopically
 pT3b Macroscopically (extravesical mass)

T4 Tumor invades any of the following: prostatic stroma, seminal vesicles, uterus, vagina, pelvic wall, abdominal wall

 T4a Tumor invades prostatic stroma, uterus, vagina
 T4b Tumor invades pelvic wall, abdominal wall

Regional Lymph Nodes (N)

Regional lymph nodes include both primary and secondary drainage regions. All other nodes above the aortic bifurcation are considered distant lymph nodes.

NX Lymph nodes cannot be assessed

N0 No lymph node metastasis

N1 Single regional lymph node metastasis in the true pelvis (hypogastric, obturator, external iliac, or presacral lymph node)

N2 Multiple regional lymph node metastasis in the true pelvis (hypogastric, obturator, external iliac, or presacral lymph node metastasis)

N3 LYMPH NODE METASTASIS TO THE COMMON ILIAC LYMPH NODE

5.0 ELIGIBILITY CRITERIA

Each of the criteria in the following section must be met in order for a patient to be considered eligible for registration. Use the spaces provided to confirm a patient's eligibility. For each criterion requiring test results and dates, please record this information on the **S1011** Prestudy Form and submit to the Data

Operations Center in Seattle (see [Section 14.0](#)). Any potential eligibility issues should be addressed to the Data Operations Center in Seattle at [name] prior to registration.

In calculating days of tests and measurements, the day a test or measurement is done is considered Day 0. Therefore, if a test is done on a Monday, the Monday 4 weeks later would be considered Day 28. This allows for efficient patient scheduling without exceeding the guidelines. **If Day 28, 56 or 70 falls on a weekend or holiday, the limit may be extended to the next working day.**

Step 1 (Registration)

5.1 Disease-related Criteria (Step 1)

- a.** Patients must have histologically-proven (T2, T3, or T4a) urothelial carcinoma of the bladder (UCB) that requires primary radical cystectomy for definitive treatment. Patients must not have clinical stage consistent with a low-risk of node metastasis (CIS only, T1). Patients with a T4b (fixed lesion) are not eligible for this study.

NOTE: Patients with predominant urothelial carcinoma with elements of adenocarcinoma, squamous cell carcinoma, micropapillary or minor components of other rare phenotypes are eligible. Patients with predominantly small cell, squamous cell, or adenocarcinoma histologies are not eligible. Patients with other non-urothelial cancers are not eligible (e.g., sarcoma, lymphoepithelial, nested variant).

Clinical stage is based on all of the following: TURBT(s) that determined the need for cystectomy, bimanual exam and cross sectional imaging.

- b.** There must be plans for the cystectomy and lymph node dissection (LND) to be performed within 28 calendar days following registration. Laparoscopic surgery is not allowed.
- c.** Surgery must be planned to be performed by a pre-approved, study-specific credentialed surgeon (see [Section 12.1](#) for credentialing process). The registering physician MUST be the pre-approved, credentialed surgeon intended to perform the assigned procedure.
- d.** Patients must not have undergone a prior partial cystectomy for invasive bladder cancer. Patients must not have received any prior pelvic surgery that would obviate a complete extended lymphadenectomy (e.g. aorto-femoral/iliac bypass) or for whom the surgeon feels that their ability to perform a standard or extended pelvic node dissection would be compromised.

5.2 Prior Therapy Criteria

- a.** Prior neoadjuvant chemotherapy for this cancer is permitted however patients must have completed treatment within 70 days prior to cystectomy and recovered from all associated toxicities at the time of registration.
- b.** Patients must not have received any prior pelvic irradiation.
- c.** Patients must have no evidence of visceral or nodal metastatic disease proximal to the common iliac bifurcation on 2 view chest x-ray or CT of the chest and abdominal-pelvic imaging with computerized tomography or MRI of the abdomen and pelvis. Chest x-ray or CT of the chest and CT or MRI of the abdomen and pelvis must be obtained within 56 days prior to registration. PET/CT may be used as an alternative to CT or MRI or to resolve possible areas of metastases seen on cross sectional imaging.

5.3 Clinical/Laboratory Criteria

- a. Patients must have bilirubin, SGOT, SGPT and alkaline phosphatase values within the institutional upper limit of normal (ULN). These laboratory values must be obtained within 28 days prior to registration. Patients with levels of one or more of these enzymes greater than IULN may still be enrolled if metastatic disease is excluded with appropriate imaging which may include dedicated liver imaging, bone scan, PET, CT, MRI, or biopsy when appropriate.
- b. Patients must have a complete physical examination and medical history within 28 days prior to registration.
- c. **Choose one of the following 2 o** Patients must have a Zubrod performance status (see [Section 10.5](#)) of 0, 1, or 2 and in the registering physician's opinion be medically suitable to undergo cystectomy.**ptions:**
- d. Women must not be pregnant or nursing at the time of radical cystectomy since the surgery and prolonged general anesthesia would place the fetus at considerable risk for demise. The prolonged recovery and debility of the patient would severely limit the patients' ability to nurse and care for an infant.

Women of reproductive potential must agree to use an effective contraceptive method at the time of radical cystectomy, throughout the surgical recovery period, and during post-operative neoadjuvant chemotherapy (if clinically indicated). A woman is considered to be of "reproductive potential" if she has had menses at any time in the preceding 12 consecutive months. In addition to routine contraceptive methods, "effective contraception" also includes heterosexual celibacy and surgery intended to prevent pregnancy (or with a side-effect of pregnancy prevention) defined as a hysterectomy, bilateral oophorectomy or bilateral tubal ligation. However, if at any point a previously celibate patient chooses to become heterosexually active during the time period for use of contraceptive measures outlined in the protocol, she is responsible for beginning contraceptive measures.

- e. No other prior malignancy is allowed except for the following: adequately treated basal cell or squamous cell skin cancer, in situ cervical cancer, adequately treated Stage I or II cancer from which the patient is currently in complete remission, or any other cancer from which the patient has been disease-free for 5 years.

5.4 Specimen Submission Criteria

- a. Patients must be offered the opportunity to participate in specimen banking for future use to include the translational medicine studies outlined in [Section 15.0](#).

5.5 Regulatory Criteria

- a. Patients or their legally authorized representative must be informed of the investigational nature of this study and must sign and give written informed consent in accordance with institutional and federal guidelines.
- b. As part of the OPEN registration process (see [Section 13.4](#) for OPEN access instructions), the treating institution's identity is provided in order to ensure that the current (within 365 days) date of institutional review board approval for this study has been entered in the system.

Step 2 (Randomization)

Patients must meet all of the criteria in Step 1 above and be registered to the study in order to be eligible for Step 2 (Randomization). Randomization will occur at the time of surgery following complete intra-abdominal and pelvic exploration ruling out visceral metastatic disease and gross nodal disease in the extended template (common iliac, pre-sciatic [fossa of Marseilles], pre-sacral, para-aortic, pre-aortic, pre-caval, para-caval) nodes.

5.6 Disease-related Criteria (Step 2)

- a. Patients must not have intra-operative evidence of pelvic lymph node involvement (confirmed by frozen section) at or above the bifurcation of the common iliac vessels in any of the extended template. **Rationale:** Failure to excise lymph nodes with known cancer involvement would be a substantial deviation from standard of care or may be a cause for abandoning the operation in favor of systemic chemotherapy.
- b. Patients must not have intra-operative evidence of T4b disease.

6.0 STRATIFICATION FACTORS

Patients will be randomized using a dynamic balancing algorithm (30) with stratification based on:

- a. Neoadjuvant chemotherapy: Cisplatin based, vs. Carboplatin based, vs. Other, vs. none.
- b. Clinical stage T2 vs. T3 or T4a. NOTE: Clinical stage is based on all of the following: TURBT(s) that determined the need for cystectomy, bimanual exam and cross sectional imaging.
- c. Zubrod performance status: 0-1 vs. 2.

7.1 Timing of Randomization

Randomization will be done at the time of surgery after the exploration in order to eliminate any bias in interpretation of the findings of the intra-operative exploration and to minimize drop-outs due to a positive finding of metastatic disease outside the standard node dissection template. After surgical exploration of the abdomen and pelvis and the absence of visceral metastatic and gross positive nodes in any of the extended template fields, surgery will then proceed according to randomization assignment.

7.2 Treatment

a. Standard Pelvic Lymph Node Dissection

All potential lymph node bearing tissue to include a complete dissection of the external and internal iliac and obturator lymph nodes. All potential node bearing tissue should be removed within the following boundaries: laterally the genitofemoral nerve; distally Cooper's ligament to include the lymph node of Cloquet; proximally the common iliac (CI) bifurcation; medially the bladder to

include the tissue medial to the hypogastric artery; and posteriorly the floor of the obturator fossa with circumferential mobilization of the external iliac artery and vein unless contraindicated due to extensive atherosclerotic vascular disease.

b. Extended Pelvic Lymph Node Dissection

This includes the standard pelvic lymph node dissection described in [Section 7.2a](#) plus bilateral common iliac nodes to include the node bearing tissue in the pre-sciatic region (fossa of Marseilles), pre-sacral nodes including the node bearing tissue anterior to the left common iliac vein and medial to the common iliac arteries up to the bifurcation of the aorta. The node dissection may be extended proximal to the aortic bifurcation up to the inferior mesenteric artery (IMA) to include the distal paracaval, pre-caval, pre-aortic and paraaortic lymph nodes according to surgeon preference.

7.3 Adherence to Recommendations for Adjuvant Chemotherapy

For patients who did not receive neoadjuvant chemotherapy, post operative adjuvant chemotherapy for pT any, N+ or pT3-4, N0 is strongly recommended but not required and will be left up to the treating physician. The Study Chairs will review the records of all patients enrolled to assess adherence to this recommendation. Non-compliance with this recommendation will be addressed by inquiry with the site physicians and coordinators.

7.4 Submission of Lymph Nodes

At a minimum the standard pelvic lymph node dissection will be submitted to the institutional pathologist for routine histology in two separate packets labeled left and right pelvic. The extended pelvic lymph node will be submitted in a minimum of 3 packets labeled left and right common iliac (including the tissue dissected from the fossa or Marseilles - also referred to as pre-sciatic) and pre-sacral. If the nodes are dissected from the bifurcation of the aorta proximally then these will be submitted as a separate packet(s). All of these regions may be submitted in smaller packets (e.g. external iliac, obturator, internal iliac) at the surgeon's preference. The [S1011](#) Intra-Op Surgical Assessment Form describing the node packet submission to pathology must be completed and submitted to the Data Operations Center in Seattle per [Section 14.4b](#).

7.5 Criteria for Removal from Protocol Treatment

- a. Intra-operative complication requiring immediate completion or termination of surgery such as myocardial infarction or serious vascular injury.
- b. When the patient is off protocol treatment and [S1011](#) Surgeon's 90-Day Assessment Form Standard Versus Extended LND has been submitted.
- c. The patient may withdraw from the study at any time for any reason.

7.6 Discontinuation of Treatment

All reasons for discontinuation of treatment must be documented in the study forms.

7.7 Follow-Up Period

All patients will be followed for recurrence and survival for a maximum of 6 years after Step 2, Randomization or until death (whichever occurs first).

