11.0 STATISTICAL CONSIDERATIONS

11.1 Accrual Goal

We anticipate that 113 eligible patients will be randomized per year to this study on a group-wide basis. We will also assume that 10 percent of enrolled patients will be found to be clinically or pathologically ineligible and hence, not randomized so our Step 1 sample size will be inflated to account for this. Based on an extensive review of the contemporary literature (see [Section 2.0, Table 1](#)), we estimate that 3-year disease free survival (DFS) for patients at increased risk for pelvic and iliac node metastasis undergoing a standard pelvic lymphadenectomy is 55%. A poll of centers of excellence suggest that a 10-12% improvement in 3-year DFS (65-67%) for patients in extended lymphadenectomy would be meaningful and establish extended node dissection as the standard of care in this patient population. Assuming exponential survival, 5 years of patient accrual, 3 additional years of follow-up and a sample size of 564 eligible patients (282 per arm), the study has 85% power to detect a 28% reduction in the hazard rate of progression or death with extended lymph node dissection compared to limited

dissection (hazard ratio 0.72). This corresponds to an improvement in 3-year DFS from 55% to 65% or alternatively median DFS would be extended from 3.5 to 4.8 years if the DFS distributions are exponential. We will use a one sided stratified log rank test with $\alpha = 0.025$, and the analysis will be intent-to-treat.

Assuming an ineligibility rate of 10%, total accrual (eligible + ineligible patients) to the initial step is expected to be 620 patients.

As a secondary endpoint, overall survival is also of great interest. If extended lymph node dissection is found to be statistically significantly better than standard lymph node dissection with respect to DFS, then an analysis of the survival endpoint will follow. We will allow for three more years of follow-up after the primary analysis has been conducted to assess potential survival differences. If we assume that the standard arm has 5-year survival of 55% then we will have 83% statistical power to detect a hazard ratio of 0.72 (55% vs. 65% survival at 5 years) using a one-sided stratified logrank test with alpha=0.025.

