If this trial continues past the two feasibility assessments, three formal interim analyses are planned to evaluate the efficacy of extended lymph node dissection. The first will be conducted after 25% of the expected events (relapse or death without relapse) have been reported on the control arm. The second after 50% of the events have occurred on the control arm, and the third when 75% of the expected events have occurred on the control arm. See the [table](#) for number of events and expected time when events will occur. The interim analyses will be conducted based on the number of events in the standard LND arm and not the estimated calendar time. Estimated number of events in the experimental arm are provided for descriptive purposes only. At each interim analysis, evidence suggesting early termination of the trial and a conclusion that the extended lymph node dissection is no better than standard dissection would be if the alternative hypothesis of a 28% improvement in DFS with the experimental arm is

rejected at the 0.005 level, using an extension of the logrank test that allows for testing a relative risk not equal to 1. In addition, the null hypothesis of no difference in DFS will be tested at the one-sided level of 0.005. If the decision is to continue the study for the full specified period, we estimate the final analysis will occur approximately three years after completion of accrual. The final DFS analysis will be conducted when 184 events have been observed on the standard LND arm, using a one-sided stratified logrank test with a significance level of 0.022 to account for multiple interim testing.

If the DFS analysis is statistically significant, the survival analysis will follow approximately two years later when 166 deaths have occurred on the control arm. The stratified logrank test will be performed at the one-sided 0.025 level.

Interim Analysis	Anticipated Analysis Time Relative to Study Activation	Percent of Expected Information On Control Arm	# of Events in the Control Arm (Standard LND)	Anticipated # of Events on Experimental Arm (Extended LND) (assuming the alternative hypothesis)
1	38 months	25%	46	34
2	56 months	50%	92	70
3	73 months	75%	139	108

With 282 eligible patients randomized to each arm, estimates of morbidity and toxicity frequencies can be estimated to within \pm 6% (95% confidence interval).

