14.4 Data Submission Overview and Timepoints

- a. WITHIN 7 DAYS OF STEP 1, REGISTRATION:

Submit the following:

S1011 Prestudy Form

Operative Report from TURBT

Pathology Report from TURBT

Radiology reports from cross-sectional imaging performed to determine the pre-REG clinical T stage, e.g. CT, MRI, or PET/CT.

- b. WITHIN 14 DAYS OF SURGERY, FOR ALL PATIENTS RECEIVING ON-STUDY SURGERY:

Submit copies of the following:

S1011 Intra-Op Surgical Assessment Form Standard Versus Extended LND

Intra-Op Photos

(Note: The Photo Upload Form is located in the data submission section of the SWOG CRA Workbench in the **S1011** Reg 2 folder under the 'Follow Up' tab. Photos should be obtained after the randomization and surgical assessment).

Operative Report from cystectomy

Pathology Report from cystectomy

- c. IF PATIENT CONSENTED, WITHIN 28 DAYS OF RANDOMIZATION:

Submit specimens as outlined in [Section 15.0](#).

- d. IF PATIENT NOT ELIGIBLE OR NOT CONTINUING TO STEP 2 RANDOMIZATION, WITHIN 14 DAYS AFTER GOING OFF STUDY:

S1011 Pre-Randomization Off Study Form

S1011 Intra-Op Surgical Assessment Form Standard Versus Extended LND
(Note: No Intra-Op photos are required for patients not going on to Step 2, Randomization)

e. WITHIN 7 DAYS FROM HOSPITAL DISCHARGE:

S1011 Surgeon's Post-Op Data Form Standard Versus Extended LND

S1011 Adverse Event Form

f. WITHIN 90 DAYS POST-SURGERY

S1011 Surgeon's 90-Day Assessment Form Standard Versus Extended LND

S1011 Adverse Event Form

g. AFTER SURGERY, EVERY THREE MONTHS FOR YEAR ONE; EVERY SIX MONTHS FOR YEARS TWO AND THREE; AND ANNUALLY UNTIL SIX YEARS AFTER RANDOMIZATION OR UNTIL DEATH:

Submit copies of the **S1011** Follow Up Form
(via the Medidata Rave® clinical data management system)

h. WITHIN 4 WEEKS OF KNOWLEDGE OF DEATH:

Submit the Notice of Death **and a final S1011** Follow Up Form.
(via the Medidata Rave® clinical data management system)

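### The six-year follow-up cap puts the survival trigger of 166 control-arm deaths out of reach under the plan's own assumptions and limits survival power to about 75%, not 83%

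*Combined protocol and SAP*

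**What the plan says.** Three places end follow-up at six years from randomization:

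- Section 7.7: "All patients will be followed for recurrence and survival for a maximum of 6 years after Step 2, Randomization or until death". The limit names survival, so it is not only a limit on visits or imaging.
- Section 9.0: the last column of the study calendar is month 72.
- Section 14.4g: follow-up forms are due "ANNUALLY UNTIL SIX YEARS AFTER RANDOMIZATION OR UNTIL DEATH".

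Section 10.4 censors living patients at last contact. No section schedules vital-status contact after year 6. The death notice in Section 14.4h is due only once a site learns of a death.

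Section 11 plans overall survival on a longer horizon, and in two ways:

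- Section 11.1: "We will allow for three more years of follow-up after the primary analysis has been conducted to assess potential survival differences". It assumes 55% control survival at 5 years and says "we will have 83% statistical power to detect a hazard ratio of 0.72", at one-sided 0.025.
- Section 11.2: if DFS is significant, "the survival analysis will follow approximately two years later when 166 deaths have occurred on the control arm".

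**The concern.** With 5 years of accrual and 3 years to the DFS analysis, two or three further years place the survival analysis at year 10 or 11. The earliest patients would then contribute 10 or 11 years of follow-up, but Section 7.7 stops them at 6. Deaths after year 6 are not systematically collected, so both the death count that triggers the analysis and the stated power may rest on deaths the trial will not observe.

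Overall survival is the first-listed secondary objective. If DFS is positive, the survival analysis would either wait for a trigger that does not arrive or be run at a time chosen after the DFS result is known, with less power than stated.

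Sections 11.1 and 11.2 also give different waiting times, three years and about two, for the same analysis.

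**Working it through.** **Inputs** (Section 11.1 unless noted): exponential survival; 282 patients per arm; 5 years of accrual, taken as uniform; 5-year survival 55% versus 65%, HR 0.72; one-sided alpha 0.025; 6-year cap (Section 7.7). The plan states no loss to follow-up, so it is set to zero, which favours the plan.

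**Hazards.** Control: λ₀ = −ln(0.55)/5 = 0.1196 per year. Extended: λ₁ = 0.72 × λ₀ = 0.0861. The ratio ln(0.65)/ln(0.55) = 0.7206 confirms the HR.

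**Expected deaths at year T.** Without a cap: 282 × [1 − (e^(−λ(T−5)) − e^(−λT))/(5λ)]. With the cap, each patient's follow-up is the smaller of 6 years and T minus entry time.

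**Power (Schoenfeld).** Φ(|ln 0.72| × √D / 2 − 1.96), where D is total deaths. Freedman replaces the first term by √D × (1 − 0.72)/(1 + 0.72).

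**Step 1: reproduce the plan without the cap.** For the control arm at year 10: 282 × [1 − (0.5500 − 0.3025)/0.5978] = 165.3, which matches the 166 in Section 11.2. At year 11 the count is 178.4, and power is 84.0% (Schoenfeld) or 83.4% (Freedman), which matches the 83% in Section 11.1.

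**Step 2: apply the cap.** Once every patient has reached 6 years:

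- Control: 282 × (1 − 0.55^(6/5)) = 282 × 0.512 = 144.4
- Extended: 282 × (1 − 0.65^(6/5)) = 113.8
- Total 258.1; power Φ(0.3285 × √258.1 / 2 − 1.96) = Φ(0.679) = 75.1%

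| Analysis | Control deaths | Extended deaths | Total | Schoenfeld | Freedman |
|---|---|---|---|---|---|
| Year 10, no cap | 165.3 | 133.0 | 298.3 | 81.0% | 80.3% |
| Year 11, no cap | 178.4 | 145.3 | 323.7 | 84.0% | 83.4% |
| Year 10, cap | 142.7 | 112.3 | 254.9 | 74.6% | 73.9% |
| Year 11 or later, cap | 144.4 | 113.8 | 258.1 | 75.1% | 74.4% |

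A log-rank simulation (4,000 runs per setting) with the cap gave about 74% power at years 10 and 11.

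**Step 3: how far away is 166?** The shortfall is 166 − 144.4, about 22 deaths. With 282 control patients and death probability 0.512, the binomial chance of 166 or more is about 0.6%. To expect 166 under the cap, 5-year control survival would have to be (1 − 166/282)^(5/6) = 47.7% or lower. At 55% survival, every control patient would need −ln(1 − 166/282)/0.1196 = 7.4 years of follow-up. Counting all 620 registrations (310 per arm) gives only 310 × 0.512 = 159.

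**Step 4: the two waiting times.** Without the cap, 166 control deaths fall at year 10.05, about two years after the DFS analysis, with power near 81%. The 83% needs 315 (Schoenfeld) to 321 (Freedman) total deaths, which fits three more years. The 166 deaths belong to one schedule and the 83% to the other.

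**Step 5: effect on DFS.** With 3-year control DFS of 55%, year 8 gives 183.8 control events without the cap, matching the planned 184, and 177.8 with it. The capped count still reaches 184 at about year 8.5 (its maximum is 196.7). Power at one-sided 0.022 is then 83.9%, the same as at year 8 without the cap.

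**The case against.** The strongest reply concerns weight. The affected analysis is secondary and runs only if DFS is significant. The primary endpoint keeps its event target, alpha and power. A six-year cap is a legitimate choice, and a survival test on capped data is valid. All of this stands: the fault is that Section 11 was not calculated for the follow-up that Section 7.7 allows.

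The trigger is also unreachable only in expectation at 55% survival. Table 2 in Section 2.0 lists 5-year survival from 45% to 66%. At 45%, the capped control arm would give 282 × (1 − 0.45^(6/5)) = 174 expected deaths and about 83% power. That is correct, but 45% comes from one series; the others in Table 2 report 58% to 66%, where the shortfall is larger than at 55%. The plan chose 55%, and its trigger and power should agree with that choice.

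The two waiting times can be read as an allowance and a projected date. Even so, the stated 83% does not go with 166 control deaths.

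Finally, the DFS effect should not be overstated. The final DFS analysis is event-driven, so the cap delays it by about six months and does not weaken it.

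**Conclusion.** The concern holds. Under the plan's own assumptions, the six-year cap limits the control arm to 144 expected deaths, about 22 short of the 166 that trigger the survival analysis, with about a 0.6% chance of reaching it. Survival power is at most about 75% (74 to 75% depending on method) against the stated 83%, so the type II error is near 25% and not 17%.

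This rests on exponential survival, uniform accrual, 282 patients per arm, 55% control survival at 5 years and no loss to follow-up. Any loss lowers the figures further. The trigger is attainable in expectation only if 5-year control survival is 47.7% or lower. The primary DFS analysis is delayed, not compromised.

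**What to change.** Reconcile Sections 7.7, 9.0 and 14.4g with Sections 11.1 and 11.2 in one of two ways:

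- **(a) Keep the cap.** State that the survival analysis takes place when all patients have completed six years, with about 144 control deaths (258 in total) and about 75% power. This changes wording only; the price is a less favourable stated power.
- **(b) Extend survival follow-up.** Collect annual vital status beyond year 6 until the survival analysis, with no added visits or imaging. The cost is a yearly contact and a protocol amendment. Consent may also need revision; the consent pages were not available to check.

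In either case, give one follow-up duration in Sections 11.1 and 11.2, with the death count and power that belong to it. Without the cap these are about 165 control deaths and 81% power at two more years, or about 178 and 84% at three. If the cap stays, also note in Section 11.2 that the 184th control-arm DFS event is expected at about year 8.5. The choice should be made before the earliest patients pass year 6, because follow-up that has lapsed is hard to recover.
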